	
Subjects will commence screening procedures within 30 days prior to randomization to confirm that they meet the selection criteria for the study.
 
At Screening V1, assessments will include informed consent, a review of demography, medical history (including COPD, smoking, and COPD exacerbation history) and concomitant medication, a physical examination, supine or semi-recumbent vital signs, supine or semi-recumbent 12-lead ECG, laboratory safety tests, pregnancy test (if required), and a chest X-ray (unless obtained within the previous 12 months). Subjects who are on a LAMA-containing treatment for their COPD will be required to have a washout of at least 7 days prior to undergoing an ipratropium reversibility test at Visit 2. However, for subjects who are not on LAMAs and who have observed the appropriate washout for other concomitant medications (e.g., 48 hours for oral leukotriene antagonists and systemic anti-muscarinics, 6 hours for short-acting beta-agonists and anti-muscarinics), V2 procedures (i.e., pre- and post-bronchodilator spirometry for FEV1/FVC measured as part of an ipratropium reversibility test) may be conducted on the same day as Visit 1.
 
After completion of V2 procedures, subjects will be discharged from the clinic with salbutamol as rescue medication and a diary card to record rescue medication use and return 7 (± 3) days later for V3.
 
Subjects who are eligible to be randomized to the study will undergo the procedures below during the 12-week treatment period (V3-V6).
 
Admission procedures for each visit: On admission at V3 to V6 the Investigator should check if the appropriate washout period has been met for use of rescue medication or other restricted concomitant medications. If not, then the visit should be rescheduled within the protocol-specified timeframe.
 
Subjects should first complete the patient reported outcomes questionnaires (PRO) - BDI/TDI, Modified Medical Research Council Dyspnea Scale (mMRC), SGRQ (in that order) - at the following visits: BDI/TDI: BDI at V3 and TDI at V4, V5, and V6 mMRC: at V3 SGRQ: at V3 and V6
 
After completion of PROs, AEs, concomitant medication use, and rescue medication use since the previous visit should be reviewed.
 
Rescue medication: Salbutamol (100 mcg) pressurized metered dose inhalers (pMDI) will be provided as rescue medication to all subjects. Subjects will record the use of salbutamol rescue medication (number of puffs daily) in a diary card which will be reviewed by the Investigator and recorded in the CRF. If a subject has used rescue medication on the same day as the clinic visit, prior to spirometry assessments, then both the number of puffs and the time of administration will be documented to allow evaluation of impact, if any, on spirometry measurements. Please note that if subjects have used rescue medication within 6 hours prior to spirometry, then the visit should be rescheduled.
 
Vital signs and 12-lead ECG: Supine or semi-recumbent blood pressure, pulse rate, and 12-lead ECG (single measurement) will be measured pre-dose and approximately 1 hour post-dose at

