Study drug will be administered using a centrally-provided, standard jet nebulizer (PARI LC Sprint) and compressor (PARI TurboBOY) via a mouthpiece. Prior to the first dose on Day 1, subjects (and their caregiver, if applicable) will be trained on the use and maintenance of the nebulizer and compressor. Study drug administration will be performed at the Investigator site at V3, V4, V5 and V6. It will take up to approximately 10 minutes and completion will be evidenced by spluttering of the nebulizer. Dosing time will be recorded in date, hours, and minutes corresponding to the start and completion of nebulization. Pre-dose assessment time is defined relative to the start of nebulization. Post-dose assessment time is defined relative to the completion of nebulization. Subjects who are on concomitant LABA or ICS/LABA should take their regular morning dose after pre-dose spirometry and immediately prior to study drug administration (if a subject takes their LABA or ICS/LABA prior to the pre-dose spirometry, the visit should be rescheduled). Between visits, study drug will be self-administered at home every morning at approximately the same time within the window of 06:00 and 11:00. The time of home administration will be recorded by the subjects in their diary. Study drug compliance will be checked by counting used and unused vials returned to the site at each visit to ensure that it is within 80-120%. Study drug administration must be performed in a different room from that used for PK blood sampling and processing to avoid contamination of PK samples.

	
Discharge procedures for each visit: Prior to discharge from the clinic at V3 to V5, subjects will be dispensed sufficient rescue medication, study drug supplies, and diary cards (for recording rescue medication and study drug administration).  At V6 only, a general physical examination will be performed prior to discharge.
 
Follow-up: A follow-up telephone call will be conducted 7-14 days after V6 to review adverse events and concomitant medication.

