## **REVISION HISTORY**

Version No.	Effective Date	Summary of Change(s)
1.0	14 Dec 21	New document
1.1	21 Jan 22	Corrected the items weight in Appendix 6.7.1 for question 14.
		Added description in Section 4.11.5 to describe algorithms of handling multiple ECG measurements performed at the same visit: the average of results used for continues variables, the worst result used for categorical variables.
	05 Feb 22	Corrected table number in Section 4.10
	15 Feb 22	Section 4.3.3, for the rule handling multiple records, Added "earliest" to illustrate that if there are multiple records are nearest, the earliest one will be used.
	27 Mar 22	Removed duplicate 'X' in Appendix 6.6
	10 May 22	Corrected the 'contrast' statement to 'estimate' statement for the model based average generation in Section 4.10.3.8 and 4.10.3.9
		Corrected table number in Appendix 6.3
	13 Jul 22	Corrected spelling in Section 3.2.1
	10 Oct 23	Section 4.10.1.5, Examination of Subgroups
		Added subgroup analysis by ethnicity:
		North East Asian verses South East Asian
2.0	16 Oct 23	Finalized for final analysis

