## 4.3.3 Analysis Windows

The summary tables will only include the assessments at scheduled visits, except the spirometry measurements. Unscheduled assessments will be included in the listings.

Unscheduled spirometry measurements with study medication taken on the same day will be mapped to corresponding visit and timepoint according to Table 4 and Table 5. Unscheduled spirometry measurements with no study medication taken on the same day will not be mapped. Spirometry measurements at an early termination visit will be mapped to the schedule visit according to Table 4.

If multiple visits fall within a window, the earliest visit with acceptable spirometry data nearest to the scheduled day will be included in the analysis.

Visit (Day) in Protocol	Analysis Visit	Target Study Day	Visit Window
Visit 3 (1)	Day 1 (Baseline)	1	1
Visit 4 (29±7)	Day 29	29	$2 \leq$ Study Day $\leq 43$
Visit 5 (57±7)	Day 57	57	$44 \leq \text{Study Day} \leq 71$
Visit 6 (85±7)	Day 85	85	$72 \leq $ Study Day

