## 6.8 Best Test Result (BTR)

The BTR process is designed to deselect any unacceptable efforts that are being used to represent the Best value for a particular measurement or reselect good quality efforts that were deselected by the Principal Investigator. If the Principal Investigator did not disregard the unacceptable efforts, the Best value could be influenced due to the fact that the MasterScope will report the highest value for FEV1 and FVC per measurement as the Best value regardless of the quality efforts.

The Best value definition in Forced Spirometry is the highest values of  $FEV_1$  and FVC of the efforts submitted by the investigative site. The goal for BTR is to ensure that only acceptable efforts are used to determine these Best values. The data submitted to the sponsor after BTR will include the highest value (FEV1 or FVC) reported from acceptable efforts. If there are no acceptable efforts available for a measurement then the data submitted will be unacceptable quality for that measurement.

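### SAP 4.3.3 chooses between repeat attendances with no washout criterion, so a trough that failed withholding can be kept over its compliant repeat in the primary analysis

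*SAP*

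**What the plan says.** **Protocol.** Two rules in the synopsis protect the trough from recent bronchodilator use. For salbutamol, "if subjects have used rescue medication within 6 hours prior to spirometry, then the visit should be rescheduled". For long-acting beta-agonists, "if a subject takes their LABA or ICS/LABA prior to the pre-dose spirometry, the visit should be rescheduled". The synopsis spirometry paragraph extends this to the other restricted medications and asks for the new date to fall within the visit window. Section 5.7 gives the LABA rule in more detail and has the puffs and time of same-day rescue recorded, so that any effect on spirometry can be evaluated.

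**SAP.** Section 4.3.3 governs which record is analysed. For unscheduled spirometry, "Unscheduled spirometry measurements with study medication taken on the same day will be mapped to corresponding visit and timepoint", whereas "Unscheduled spirometry measurements with no study medication taken on the same day will not be mapped". When more than one attendance qualifies, "If multiple visits fall within a window, the earliest visit with acceptable spirometry data nearest to the scheduled day will be included in the analysis". The revision history explains the word earliest as a tie-break: "if there are multiple records are nearest, the earliest one will be used". On what makes spirometry acceptable, SAP 6.8 says "The goal for BTR is to ensure that only acceptable efforts are used to determine these Best values". Protocol 6.4.2 likewise speaks of faults such as hesitation or cough.

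SAP 4.4.2 lists rescue use within 6 hours of spirometry as a possible major deviation, which bears on the per-protocol set. SAP 4.10.2.1 runs the primary MMRM on the FAS.

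**The concern.** The protocol treats withholding as a condition for a valid trough, but the SAP's selection rule does not. A subject who fails withholding, has FEV1 recorded anyway and then returns for a compliant repeat will have two candidate troughs in one window. The repeat exists only because the first was judged unsuitable, yet the rule ranks the two by calendar distance alone once both pass over-read.

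At stake is which value supplies the change from baseline at Days 29, 57 and 85, and so the Day 85 contrast. If rescue use is more common on placebo, which is an assumption, selected failed troughs would tend to raise the placebo mean and narrow the difference. The trial is meant as a bridge to the US pivotal results, which protocol 2.2 gives as 146.26 and 147.01 mL, so the size of the estimate matters as well as its significance.

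**Working it through.** The point contests no figure in the plan. The yardstick is the planned 100 mL difference, and it reproduces: 2 × (1.960 + 1.282)² × 245² / 100² = 126.1, so 127 per arm by the normal formula. The stated 128 per arm gives power 0.904.

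**Step 1. Do both attendances share a window?** The protocol visit windows are Days 22–36, 50–64 and 78–92. The SAP Table 4 windows are Days 2–43, 44–71 and 72 onward. Each protocol window lies wholly inside one SAP window, so a repeat made within the visit window always competes with the first attendance.

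**Step 2. Does any filter remove the failed attendance?**
- Same-day study drug applies only to unscheduled spirometry. A subject on daily morning dosing can meet it after being sent home.
- SAP Table 5 puts no lower limit on the −45 minute slot (anything before −30 minutes), so a reading taken well before a later home dose still maps to pre-dose.
- SAP 4.10.2 lets one pre-dose reading stand as the trough.
- Over-read judges the manoeuvre, not medication timing.
- The deviation list in SAP 4.4.2 serves per-protocol exclusion and does not alter the FAS. Early LABA use is not named in it, although the list is open-ended.

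None of these screens for washout.

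**Step 3. Which attendance does the rule pick?** Let *o* be the offset in days of the failed first attendance from target and *n* that of the repeat, with −7 ≤ *o* < *n* ≤ +7. There are 15 × 14 / 2 = 105 pairs. The first attendance is selected when |*o*| ≤ |*n*|.
- *o* ≥ 0: every later day is farther away, so the first is always selected. Pairs: 7 + 6 + 5 + 4 + 3 + 2 + 1 = 28 of 28.
- *o* = −k, for k = 1 to 7: the first is selected only when *n* ≥ k, which is 8 − k values. Sum: 28 of the remaining 105 − 28 = 77. Seven of these 28 are ties (*n* = k), which go to the earlier record.
- Total: 28 + 28 = 56 of 105 (53%).

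Examples at Day 85:

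| Failed | Valid repeat | Selected |
|---|---|---|
| 85 | 87 | 85 (failed) |
| 86 | 90 | 86 (failed) |
| 83 | 87 | 83 (failed, tie) |
| 80 | 84 | 84 (valid) |
| 82 | 84 | 84 (valid) |

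Days 29 and 57 give the same counts. The Day 1 window is a single day, so the rule never chooses between days at baseline.

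**The case against.** The strongest answer is that the protocol stops this before any FEV1 exists. Checking washout is the first listed step at Visits 3 to 6 (protocol 6.2.1 to 6.2.4), and the synopsis requires it on admission. A visit run as written is rescheduled with nothing recorded. The problem needs a missed check or late disclosure, an acceptable reading kept as a separate attendance, study drug the same day if that attendance counts as unscheduled, a compliant repeat, and a first date that is nearer or tied. The documents foresee spirometry after rescue use (protocol 5.7, SAP 4.4.2), but they do not describe a failed visit and a valid repeat together. This stands, and it limits how often the rule can matter. A reader might infer that the SAP undoes the protocol's safeguard; it does not, because the admission check is untouched.

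Second, the primary model is repeated in the per-protocol set, with exclusions decided blind. That offers some check on contaminated troughs. It removes the subject and does not restore the valid repeat, so it is only a partial answer.

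Third, any bias from rescue use would probably be conservative. That is fair under the assumption of more rescue on placebo, and no false efficacy claim is suggested. The argument does not extend to LABA: its use is a randomization stratum, and nothing suggests that early LABA doses differ by arm.

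**Conclusion.** The point holds in a limited form. As written, SAP 4.3.3 can select a trough that failed withholding over a compliant repeat in the same window, and it must do so when the first attendance is on or after the target day and both pass over-read. This follows from the text alone.

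How often it happens, and how far it would move the estimate, cannot be derived from the documents. Both are probably small. Three stronger readings are tempting and are not supported:
- That the failed visit wins 53% of the time. This is a count of day-pairs given equal weight, not a probability; actual scheduling is unknown.
- That the bias is 2 to 20 mL. That range comes from assuming a 100–200 mL lift and a 2–10% placebo excess of affected subjects (100 × 0.02 = 2; 200 × 0.10 = 20). Neither factor is in the documents. The 200 mL figure is part of the reversibility criterion 45 minutes after nebulized ipratropium (protocol 6.4.3), not a residual effect of salbutamol taken up to 6 hours earlier. Failed troughs with no repeat are not caused by this rule at all.
- That baseline selection is affected. The single-day window rules that out.

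The case for changing the rule is that it gives the wrong answer when the case arises and is easy to correct. It should be settled before unblinding, because choosing between two recorded troughs afterwards would be discretionary.

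**What to change.** Add to SAP 4.3.3 that, among post-baseline attendances in a window, those that met the protocol's withholding times for salbutamol, LABA and other restricted medication take precedence. The nearest-day rule, earliest if tied, is then applied within that group. If no attendance qualifies, the rule operates as now.

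The flag can be built mostly from data already collected: the recorded time and puffs of same-day rescue, and the LABA dosing record or deviation log. LABA dosing on visit days is documented in source (protocol 5.7), so the sponsor should confirm that it reaches the database or rely on the deviation log.

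Optionally, run the primary MMRM once more with post-baseline troughs that failed withholding and have no valid repeat set to missing. This addresses a neighbouring question, not the selection rule itself.

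Cost: a small programming flag and, if the optional run is done, one extra output. No visit procedure or clinical rule changes.

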#### Table 4: Analysis Windows (Days)

#### Table 5: Analysis Windows (Timepoint)

Analysis Timepoint	Time Window
-45 Min	Timepoint < -30 Min
-15 Min	-30 Min ≤ Timepoint < 0 Min
5 Min	$0 \text{ Min} < \text{Timepoint} \le 10 \text{ Min}$
15 Min	$10 \text{ Min} < \text{Timepoint} \le 22 \text{ Min}$
30 Min	$22 \text{ Min} < \text{Timepoint} \le 45 \text{ Min}$
1 H	$45 \text{ Min} < \text{Timepoint} \le 75 \text{ Min}$
1 H 30 Min	75 Min < Timepoint ≤ 1H 45 Min
2 H	1H 45 Min < Timepoint

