A single spirometry session will be conducted for pre- and post-bronchodilator measurements at Screening (Visit 2) but two pre-dose spirometry sessions will be conducted at Visit 3 (Day 1) through to Visit 6 (Day 85), with assessments at approximately -45 and -15 minutes prior to dosing (subjects should rest for at least 10 minutes between sessions).

At Visit 3 (Day 1) and Visit 6 (Day 85), all subjects will perform spirometry assessments up to 2 hours post-dose (time points 5, 15, and 30 minutes, and 1, 1.5, and 2 hours; single sessions at each time point). Spirometry should be commenced at the nominal time  $\pm 10\%$  (for example  $60 \pm 6$  minutes).

- If a subject needs to use rescue medication during the serial spirometry session, the time of dosing must be recorded and a protocol deviation documented.

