4.10.3.1 CBL Trough FEV1 and FVC

The changes from baseline trough  $FEV_1$  on Days 29 and 57 will be estimated from the MMRM analysis used for the primary analysis of the primary endpoint.

The changes from baseline trough FVC on Days 29, 57 and 85 will be analyzed using the same MMRM analysis described for the primary analysis of the primary endpoint. The baseline  $FEV_1$  covariate will be replaced with the baseline trough FVC recorded on Day 1.

4.10.3.2 CBL to Peak  $FEV_1$  (0-2h) on Days 1 and 85

Lung function assessments will be made after study treatments (5, 15, and 30 minutes, and 1, 1.5, and 2 hours) on Day 1 and Day 85. Peak  $FEV_1$  is defined as the highest post-dose  $FEV_1$  value within 2 hours after the dosing on Day 1.

Peak  $FEV_1$  on Day 1 and Day 85 will be summarized by treatment group for the actual value and for the change from baseline on Day 1.

An ANCOVA model will be used to assess the difference between treatment groups for the change from baseline to Peak  $FEV_1$  after the first dose on Day 1. The ANCOVA model will include treatment, and concomitant LABA use, reversibility to ipratropium, smoking status, age, sex, baseline  $FEV_1$  as covariates.

The difference between revefenacin and placebo on Day 1 will be estimated from the LS means along with the 95% CI and associated 2-sided p-values.

A separate analysis will be performed for Peak FEV1 on Day 85 using the same ANCOVA model.

4.10.3.3 CBL in Weighted Mean FEV1 (0-2h) on Days 1 and 85

The area under the curve (AUC) [0 to 2] hours will be calculated using the trapezoidal rule, including observed data points from the pre-dose (0 hour) through to the 2 hour observation. For all observations the nominal time of the observation should be used. For the calculation of AUC, the first (0 hour), last (2 hour) and at least one time point between first and last must be available. Otherwise, the AUC is set to missing. The Baseline FEV1 on Day 1 and Trough FEV1 on Day 85 will be used as the 0 hour data point to calculate the AUC for Day 1 and Day 85, respectively.

The weighted mean (WM)  $FEV_1$  is derived from dividing AUC by the total time (nominally 2 hours).

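### The open-ended 2 H window in SAP Table 5 lets an unscheduled FEV1 taken hours after the dose count as a 120-minute value in Weighted Mean FEV1 (0-2h)

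*SAP*

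**What the plan says.** SAP 4.3.3 excludes unscheduled assessments from the summary tables but makes an exception for spirometry. If study drug was taken on the day of an unscheduled measurement, the measurement "will be mapped to corresponding visit and timepoint according to Table 4 and Table 5". If not, it is left out: "Unscheduled spirometry measurements with no study medication taken on the same day will not be mapped".

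Table 5 gives the time windows. The post-dose rows are closed at both ends; for example, the 1 H row begins "1 H $45 \text{ Min} < \text{Timepoint" and ends at 75 minutes, and the 1 H 30 Min row is "75 Min < Timepoint ≤ 1H 45 Min". The 2 H row has a lower limit of 1 h 45 min and no upper limit.

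SAP 4.10.3.3 derives the weighted mean by the trapezoidal rule over 0 to 2 hours, divided by 2 hours. It states: "For all observations the nominal time of the observation should be used". The AUC needs a 0 h value, a 2 h value and one or more in between, and is otherwise missing.

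SAP 4.10.3.2 defines Peak as the largest post-dose reading in the first 2 hours after dosing, and words that limit for Day 1 only. For Day 85 it specifies a separate analysis with the same ANCOVA model.

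For scheduled readings, Protocol 6.4.2 sets a collection tolerance: "Spirometry should be commenced at the nominal time" plus or minus 10%.

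**The concern.** A window exists so that a reading carrying a nominal label was taken near that time. The 2 H row does not ensure this: readings at 2 h and at 8 h after the dose receive the same label. Because the weighted mean then uses the nominal time, the actual time is lost and the later reading is integrated as a 120-minute value. It can also make an AUC computable that the SAP would otherwise set to missing for want of a 2-hour value.

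At stake is whether Weighted Mean FEV1 (0-2h) on Days 1 and 85 contains only readings from the interval in its name. The Peak endpoint on the same days shares the question through its loosely specified time limit. Trough FEV1, and so the primary endpoint, uses pre-dose readings and is not touched by the 2 H row.

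**Working it through.** **1. The logic of Table 5.** The nominal post-dose times are 5, 15, 30, 60, 90 and 120 min. Midpoints of neighbouring times are (5+15)/2 = 10, (15+30)/2 = 22.5, (30+60)/2 = 45, (60+90)/2 = 75 and (90+120)/2 = 105 min. Table 5 has 10, 22, 45, 75 and 105, so its cut-offs reproduce apart from rounding 22.5 down. The table is a nearest-nominal-time rule, and the 2 H row is the one post-dose row that departs from it. Mirroring that row's lower half-width (120 − 105 = 15 min) would close it at 120 + 15 = 135 min. The protocol's 10% tolerance gives 120 × 0.9 = 108 to 120 × 1.1 = 132 min.

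**2. How late a reading labelled 2 H can be.** Dosing is between 06:00 and 11:00 (SAP 3.1.2.2), and the mapping rule requires only a dose on the same day. The theoretical limit is therefore about 24 − 6 = 18 h after a 06:00 dose, or 24 − 11 = 13 h after an 11:00 dose.

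**3. Weight of the 2 h point in the weighted mean.** Under the trapezoidal rule the last point has weight (120 − t)/2 ÷ 120, where t is the time of the preceding available point.

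- All points present (t = 90): 15/120 = 12.5%.
- Only 0 h, one intermediate point and 2 h:

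| Intermediate point (min) | Weight of the 2 h value |
|---|---|
| 5 | 57.5/120 = 47.9% |
| 15 | 52.5/120 = 43.75% |
| 30 | 45/120 = 37.5% |
| 60 | 30/120 = 25% |
| 90 | 15/120 = 12.5% |

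**4. Effect on one subject.** The documents do not say how far a late reading would lie from the true 2 h value, so the difference is assumed. At 50 mL the subject's weighted mean moves by 50 × 0.125 = 6.25 mL to 50 × 0.479 = 24.0 mL. At 100 mL it moves by 12.5 to 47.9 mL.

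**5. Effect on an arm mean.** With 128 evaluable subjects per arm (SAP 4.12), one affected subject at the 100 mL assumption moves the unadjusted arm mean by 12.5/128 = 0.10 mL to 47.9/128 = 0.37 mL. This scales with the number affected, which the documents do not give.

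**6. Peak.** Peak is a maximum. Suppose every genuine reading from 5 to 90 min is 150 mL above baseline (assumed). A late reading of +50, +100 or +150 mL leaves Peak at 150; one of +200 mL raises it to 200, but only if the label decides entry. Actual time is not an obviously safe reading either: a strict 120-minute limit would drop scheduled 2 h readings begun between 120 and 132 min, which the protocol permits.

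**7. Competing readings.** SAP 4.3.3 chooses between visits: "If multiple visits fall within a window, the earliest visit with acceptable spirometry data nearest to the scheduled day will be included in the analysis". It has no rule for several readings of one visit in the same Table 5 window. If a scheduled 2 h reading exists, use of a later one is possible but not settled. If it is missing, the late reading is the only value labelled 2 H.

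**The case against.** The strongest reply is that little can get through. Scheduled readings are held to 10% of nominal time. Peak has its own 2-hour limit. Where several visits compete, the one nearest the scheduled day is used, so an attended Visit 6 would normally displace a stray earlier visit. These points stand, and they narrow the problem to a same-visit series with no valid 2 h reading. They do not remove it, because no other rule limits the label that the weighted mean depends on.

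Three stronger readings are tempting, and the documents do not support them.

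- **That a late reading necessarily enters Peak.** The nominal-time instruction sits in the AUC paragraph, not in the definition of Peak. On a plain reading of SAP 4.10.3.2 a 5-hour value is excluded. What remains open is whether label or actual time governs, and what limit applies on Day 85.
- **That an unwell subject seen once, say on Day 78 some hours after a home dose, supplies the Day 85 result and so favours revefenacin.** One late reading gives no weighted mean, because the 0 h and intermediate values are absent. Early-termination spirometry corresponds to the pre-dose sessions (Protocol 6.2.5) and is mapped by Table 4 only. No frequencies by arm are given. Where genuine readings exist, an extra one can only raise Peak or leave it unchanged, so an excess on placebo could work against revefenacin.
- **That the -45 Min window, open at its early end, needs the same cap.** No harm is shown and the documents supply no basis for a particular bound. A cap could discard valid pre-dose values that feed trough FEV1 and the primary endpoint.

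**Conclusion.** The point holds as a minor specification error. As written, the SAP would treat an unscheduled FEV1 taken many hours after a same-day dose as a 120-minute value in Weighted Mean FEV1 (0-2h) on Day 1 or Day 85. The share of that subject's result is fixed by the trapezoidal weights, at 12.5% to 47.9%. The millilitre figures rest on assumed differences of 50 to 100 mL. Entry into Peak is an unresolved ambiguity, not an established fault. Occurrence is expected to be rare, but the documents give no rate. The direction is unknown, and the primary endpoint and sample size are unaffected.

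**What to change.** In SAP Table 5, close the 2 H row: later than 1 h 45 min, up to and including 2 h 15 min. That matches the row's own half-width; 2 h 12 min would match the protocol's 10% tolerance instead. Add to SAP 4.3.3 that unscheduled readings after this limit are listed only. In SAP 4.10.3.2, state that Peak on both Day 1 and Day 85 uses readings inside the bounded post-dose windows. Leave the -45 Min row as it is.

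The cost is one table cell and two sentences, with no change to any model or to the sample size. A few late unscheduled readings would go unused, and an occasional AUC would become missing under the SAP's existing rule. SAP 4.13 requires changes made after version 2.0 is finalised to be documented in the clinical study report, so the change should be recorded there if it comes after that point.
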